8.3.2 Unsolicited Adverse Events

All unsolicited AEs will be recorded in the study database from receipt of first study injection through 4 weeks after the last study injection administered. At subsequent follow-up visits, only SAEs and new chronic medical conditions will be recorded through the last study visit.

The proportion of subjects reporting at least one unsolicited AE will be summarized by MedDRA system organ class and preferred term for each injection, age stratum, and treatment group and over all injections. Denominators for percentages are the number of subjects who received the injection being summarized. A 95% CI will be presented along with a Fisher's exact test comparing the treatment groups and testing the difference in the proportion of subjects reporting an unsolicited AE for each MedDRA system organ class and preferred term (**Table 14.3.1.6, Appendix I**).

Unsolicited AEs by subject will be presented in **Listing 16.2.7.2, Appendix III**.

The following summaries for unsolicited AEs will be presented by MedDRA system organ class (SOC), preferred term, dose, age stratum, treatment group, and site:

- *Subject level summary of severity and relationship to study product (**Tables 14.3.1.7.1-14.3.1.7.2, Appendix I**);*
- *Subject incidence of AEs over time (Days 1-7, Days > 7) (**Tables 14.3.1.8.1-14.3.1.8.2, Appendix I**);*
- *Total frequency of AEs over time (Days 1-7, Days > 7) (**Table 14.3.1.9, Appendix I**);*
- *Subject listing of non-serious AEs of moderate or greater severity (**Table 14.3.2.2, Appendix I**);*
- *Bar chart of non-serious AEs by severity and MedDRA SOC (**Figure 14.3.1.2, Appendix II**);*
- *Bar chart of non-serious AEs by severity (**Figure 14.3.1.3, Appendix II**);*
- *Bar chart of non-serious AEs by relationship to study product and MedDRA SOC (**Figure 14.3.1.4, Appendix II**);*

- *Bar chart of non-serious AEs by relationship to study product (Figure 14.3.1.5, Appendix II).*

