3.2 Endpoints

3.2.1 Primary Endpoints

Safety

Assessment of product safety will include clinical observation and monitoring of hematological and chemical parameters. Reactogenicity will be closely monitored for 7 days after injection and safety evaluated by clinical visits through the study duration of 72 weeks.

The following parameters will be assessed:

- Local reactogenicity signs and symptoms for 7 days after each injection
- Systemic reactogenicity signs and symptoms for 7 days after each injection
- Laboratory measures of safety through 4 weeks after last injection
- Adverse events through 4 weeks after last injection
- Serious adverse events and new chronic medical conditions throughout the study
- CHIKV infection events throughout the study

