5 SAMPLE SIZE CONSIDERATIONS

The study design is to enroll 400 healthy adult participants ages 18 to 60 that reside in CHIKV endemic areas. Randomization will equally allocate subjects to vaccine or placebo schedules with electronic stratification by ages 18-40 and 41-60 years. The enrollment plan does not include provision for replacing subjects with incomplete injections or visit schedules.

Enrollments may occur rapidly at more than one site. The sample size for this study was not selected to test a formal null hypothesis, rather it reflects the number of vaccine doses that are available for the study and the desire to gain maximal information for the possible conduct of Phase 3 follow on trials. There are not good data to estimate the loss to follow-up rate for this study. The power calculations assume a 10% loss in both groups for the primary and secondary endpoints.

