6 GENERAL STATISTICAL CONSIDERATIONS

6.1 General Principles

All continuous variables will be summarized using the following descriptive statistics: n (non-missing sample size), mean, standard deviation, median, maximum and minimum. The frequency and percentages (based on the non-missing sample size) of observed levels will be reported for all categorical measures. In general, all data will be listed, sorted by site, treatment and subject, and when appropriate by visit number within subject. All summary tables will be structured with a column for each treatment in the order (Experimental, Control) and will be annotated with the total population size relevant to that table/treatment, including any missing observations.

Summary statistics for discrete data will include estimates and confidence intervals for binomial data; contingency tables, along with summary analyses such as tests of independence. Two-by-two tables may also include summaries of risk differences or risk ratios as is appropriate along with their confidence intervals.

Tabulations will be used extensively to summarize the data and will include summary statistics. For continuous data, tables will include measures of central tendency such as the mean, geometric mean, or median, and measures of dispersion such as the standard deviation or inter-quartile range. Tables of discrete data will include proportions and their confidence intervals.

Unless noted, statistical analyses will use standard methods as described below.

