 - GEE: $\sum_{i=1}^n \left(\frac{\partial P_i}{\partial \beta} \right) V_i^{-1}(\alpha) (Y_i - P_i) = 0$ where $P_i = E(Y_i)$ $V_i(\alpha)$ is the working covariance matrix;
 - Output: estimated of two intercepts from the two fitted logistic models; point estimates and 95% CI for the individual levels of the GROUP, TIME and GROUP*TIME variables, and Type-3 SAS output for the parameter significance (chi-Square test);

The study is not powered to detect differences by vaccine group, therefore the absence of statistically significantly differences should not be interpreted that no such differences exist.

Individual clinical laboratory results for hematology and chemistry will be presented in **Listing 16.2.8.1 – 16.2.8.2, Appendix III**. Laboratory summary statistics are presented in **Table 14.3.4.2, Appendix I**. Box plots for laboratory results are presented in **Figures 14.5.1 – 14.5.x, Appendix II**. A listing of abnormal laboratory results is presented in **Table 14.3.4.3, Appendix I**.

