		n	%	n	%										
Overall															
Any Local Symptom	None	x	x.x	x	x.x										
	Mild														
	Moderate														
	Severe														
	Not Reported														
[Local Symptom 1]	None														
	Mild														
	Moderate														
	Severe														
	Not Reported														
[Local Symptom 2]	None														
	Mild														
	Moderate														
	Severe														
[continue for all local symptoms]	Not Reported														
Site 1 [repeat for all sites]															
Any Local Symptom	None														

Severity is the maximum severity reported post dosing for each subject for each day.

TABLE 14.3.1.4:
Number and Percentage of Subjects Experiencing Solicited Events for Dose 1 Compared with Dose 2 by Treatment Group
Systemic Symptoms <<Overall/Site, Age Stratum>>

Treatment Group	Dose 1	Dose 2 – No Symptoms (N=X)	Dose 2 – Mild or Greater Symptom (N=X)	Dose 2 – Total (N=X)
CHIKV	No Symptoms (N=X)	x (x.xx)	x (x.xx)	x (x.xx)
	Mild or Greater Symptom (N=X)			
	Total (N=X)			
Placebo	No Symptoms (N=X)			
	Mild or Greater Symptom (N=X)			
	Total (N=X)			

Local Symptoms <<Overall/Site, Age Stratum>>

Treatment Group	Dose 1	Dose 2 – No Symptoms (N=X)	Dose 2 – Mild or Greater Symptom (N=X)	Dose 2 – Total (N=X)
CHIKV	No Symptoms (N=X)	x	x	x
	Mild or Greater Symptom (N=X)			
	Total (N=X)			
Placebo	No Symptoms (N=X)			
	Mild or Greater Symptom (N=X)			
	Total (N=X)			

TABLE 14.3.1.5:
Comparison of the Proportion of Subjects Experiencing Solicited Events by Treatment Group and Site <<Age Stratum>>

Symptom	Statistic	CHIKV Post Either Dose (N=X)	Placebo Post Either Dose (N=X)
Overall			
Any Symptom	Proportion	x.xx	x.xx
	95% CI (for proportion)	x.xx, x.xx	x.xx, x.xx
	Difference	x.xx	x.xx
	95% CI (for difference)	x.xx, x.xx	x.xx, x.xx
[Symptom 1]	Proportion		
	95% CI (for proportion)		
	Difference		
[continue for all symptoms]	95% CI (for difference)		
Site 1 [repeat for all sites]			
Any Symptom	Proportion		
	95% CI (for proportion)		
	Difference		
	95% CI (for difference)		

TABLE 14.3.1.6:
Number and Percentage of Subjects Experiencing Unsolicited Adverse Events with 95% Confidence Intervals by
MedDRA® System Organ Class, Preferred Term, Treatment Group and Dose Number <<Age Stratum>>
Post Dose 1 [Repeat for Dose 2 and Either Dose]

MedDRA® System Organ Class	MedDRA® Preferred Term	CHIKV (N=X)			Placebo (N=X)			Comparison of % subjects experiencing event (p-value) ¹
		n	%	95% CI	n	%	95% CI	
Overall								

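### Unsolicited adverse events, a primary safety endpoint, get a between-arm Fisher p-value but no committed risk difference with a confidence interval

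*Combined protocol and SAP*

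**What the plan says.** SAP 3.2.1 lists this endpoint among the primary ones: "Adverse events through 4 weeks after last injection". The primary objective (SAP 3.1) is safety and tolerability relative to placebo.

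For unsolicited events SAP 8.3.2 states: "A 95% CI will be presented along with a Fisher's exact test comparing the treatment groups". The summary is by system organ class (SOC) and preferred term (PT), for each injection and over all injections, by age stratum and treatment group. The test is described as an "exact test comparing the treatment groups and testing the difference in the proportion of subjects reporting an unsolicited AE for each MedDRA system organ class"; preferred terms are treated the same way. The text does not say what the interval refers to, but the Table 14.3.1.6 shell (SAP Appendix I) does. Each arm has its own count, percentage and 95% CI, and the single between-arm column is headed "Comparison of % subjects experiencing event (p-value". The shell repeats the layout by dose, age stratum and site. Tables 14.3.1.7.1 to 14.3.1.9 show one arm at a time, with no contrast.

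Three other places bear on this:

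- SAP 6.1: "Two-by-two tables may also include summaries of risk differences or risk ratios as is appropriate along with their confidence intervals". This is permission, and it is not tied to any table.
- Table 14.3.1.5, for solicited events, has rows for a difference and its 95% CI. Its title and its vaccine and placebo columns (after either dose) point to a between-arm contrast, although the text of SAP 8.3.1 describes Tables 14.3.1.4 and 14.3.1.5 as comparing dose 1 with dose 2.
- SAP 8.6, on laboratory data, warns that the study is not powered for group differences, "therefore the absence of statistically significantly differences should not be interpreted that no such differences exist". SAP 8.3.2 has no such sentence.

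**The concern.** The aim is to find safety concerns relative to placebo and to inform later trials. For that a reader needs the estimated excess and the range of excess compatible with the data. A p-value gives neither, and two per-arm intervals do not combine by eye into an interval for the difference. Most rows will have few events, so most p-values will be unremarkable whether or not a modest excess exists.

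The choice also sits oddly with the rest of the plan. SAP 6.8 says that no specific hypothesis is tested, yet the only comparative output for this endpoint is a test. Solicited events, part of the same primary endpoint set, have a difference and interval in their shell.

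**Working it through.** **The plan's own figure.** SAP Table 3 (protocol Table 4) gives minimum detectable differences with 180 per group, two-sided 5%. They reproduce as the continuity-corrected approximation to Fisher's test. Take 5.0% v 14.2% at 80% power, with mean rate 0.096 and difference 0.092:

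- Uncorrected n' = [1.96·√(2·0.096·0.904) + 0.8416·√(0.05·0.95 + 0.142·0.858)]² / 0.092² = (0.8166 + 0.3463)² / 0.008464 ≈ 159.8.
- Corrected n = (n'/4)·[1 + √(1 + 4/(n'·0.092))]² = (159.8/4)·(2.128)² ≈ 181, against the stated 180.

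At 80% power the table runs from 5.4 points (control rate 0.1%) to 14.3 points (25%). By the plan's own account, smaller excesses will often yield a non-significant result.

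**Inputs.** Planned size: "The study design is to enroll 400 healthy adult participants", allocated 1:1, so up to 200 per arm. SAP 8.3.2 sets the denominator: "Denominators for percentages are the number of subjects who received the injection being summarized". The planning figure after 10% loss is 200 × 0.9 = 180. The documents give no expected rate for unsolicited events, so the event counts below are assumptions, shown over a range.

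**Fisher p, 200 per arm.**

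- 4 v 0: 2 × (200·199·198·197)/(400·399·398·397) = 0.123.
- 5 v 0: multiply by 196/396, giving 0.061.
- 6 v 1: 2 × [C(200,7) + 200·C(200,6)]/C(400,7) = 0.122.

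**Miettinen-Nurminen interval.** The limits are the values d at which |D − d|/√V(d) = 1.96. Here D is the observed difference and V(d) = [p₁(1−p₁)/n + p₀(1−p₀)/n]·N/(N−1), with p₁ and p₀ the maximum-likelihood rates under p₁ − p₀ = d. Checking d = 0:

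- 4 v 0: pooled rate 4/400 = 0.01; √V = √(2·0.01·0.99/200 × 400/399) = 0.00996; 0.02/0.00996 = 2.01, so zero lies just outside.
- 6 v 1: pooled rate 7/400 = 0.0175; √V = 0.01313; 0.025/0.01313 = 1.90, so zero lies inside.

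Solving for both limits:

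| Per arm | Vaccine v placebo | Fisher p | Difference (points) | 95% CI |
|---|---|---|---|---|
| 200 | 4 v 0 | 0.123 | 2.0 | 0.1 to 5.0 |
| 200 | 5 v 0 | 0.061 | 2.5 | 0.6 to 5.7 |
| 200 | 6 v 1 | 0.122 | 2.5 | −0.1 to 6.0 |
| 180 | 18 v 9 | 0.108 | 5.0 | −0.5 to 10.9 |
| 180 | 56 v 45 | 0.241 | 6.1 | −3.2 to 15.3 |

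In the first three rows the observed excess is 2.0 to 2.5 points; 5 to 6 points is the upper limit. The last two rows show the upper limit rising with the placebo rate (5% and 25%).

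**Is an observed excess of 5 points missed?** Not at low placebo rates. With 200 per arm, 12 v 2 gives p = 0.012 and 14 v 4 gives p = 0.027. With 180 per arm, the largest observed excess with p > 0.05 is 2.8 points at zero placebo events, 5.0 at a placebo rate of 2.8%, 6.1 at 5% and 10.0 at 25%.

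**Chance findings.** Enumerating all outcomes with 200 per arm and equal true rates:

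| True rate | Fisher p ≤ 0.05 | Score CI excludes zero |
|---|---|---|
| 0.5% | 0.04% | 1.4% |
| 1% | 0.5% | about 4% |
| 2% | 1.7% | 4.5% |

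**The case against.** The strongest defence is that a per-arm display with a Fisher p-value is a conventional screen for sparse adverse-event data. Both percentages are printed, so the point difference can be read off, and SAP 6.1 already allows an interval to be added. Fisher's test also underlies SAP Table 3, so dropping it would cut the table loose from its stated operating characteristics. This stands as a reason to keep the p-value. It does not supply the interval for the difference, which no output for this endpoint commits to.

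A second objection also stands: intervals on every row carry the same multiplicity as p-values, and for rare events an unadjusted score interval excludes zero by chance more often than Fisher flags. Swapping one for the other would therefore not reduce chance signals.

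A reader might infer two stronger things. One is that Fisher's test would label an observed excess of 5 to 6 points non-significant. That is true only at placebo rates of roughly 3 to 5% or more; on rare-event rows such an excess gives p < 0.05. The other is that the plan would treat a non-significant row as evidence of no excess. The SAP sets no significance threshold for adverse events and disclaims hypothesis testing. Its caution in 8.6, although written for laboratory data, points the other way.

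**Conclusion.** The concern holds as a gap in committed reporting: the plan guarantees no estimate, with uncertainty, of the excess of unsolicited events over placebo. On rare-event rows a p-value near 0.12 can coexist with a compatible excess of up to about 5 to 6 points; at placebo rates of 5% to 25% the examples reach about 11 to 15 points. These sizes assume 180 to 200 per arm and illustrative counts. The conduct of the trial is unaffected, but the change should be made because it concerns a primary endpoint and is cheap.

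**What to change.** In SAP 8.3.2 and Table 14.3.1.6:

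1. Add a column with the vaccine-minus-placebo risk difference and its Miettinen-Nurminen 95% CI for every SOC and PT row. State that the existing CIs are per arm.
2. Keep the Fisher p-value, described as a flag.
3. State that the new intervals are unadjusted and descriptive, are not to be read as tests, and may disagree with Fisher for sparse events, as 4 v 0 shows.
4. Carry the SAP 8.6 caution on non-significance into 8.3.2.
5. While editing, align the SAP 8.3.1 text with the Table 14.3.1.5 shell.

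The cost is one more column in a long table and a few sentences; no new data are needed. The real downside is that, at a 1% true rate, about 4% of such intervals exclude zero by chance against 0.5% of Fisher p-values at or below 0.05. Item 3 is therefore essential.

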8.4 Deaths, Serious Adverse Events and other Significant Adverse Events

For reported deaths, SAEs, and new onset chronic medical conditions, the following listings will be presented:

- Deaths and SAEs (Table 14.3.2.1, Appendix I);
- New Onset Chronic Medical Conditions (Table 14.3.2.3, Appendix I).

These tables will be presented in terms of the following variables: Subject ID, Age (years), AE Description, Severity, AE Onset Date/End Date, Last Dose Received/Days Post Dose, Effect on Injection Schedule, Reason Reported as an SAE, Relationship to Treatment, Outcome, and Duration of Event (days).

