8.3 Adverse Events

The severity of an adverse event (AE) is defined as: Grade 1 (Mild), Grade 2 (Moderate), Grade 3 (Severe), Grade 4 (Life-threatening), and Grade 5 (Death). Only the single AE that is assessed as the primary cause of death should be assigned “Grade 5” severity.

Relation of an AE to the study product is defined as Definitely Related, Probably Related, Possibly Related, and Not Related. For purposes of preparing data reports in which AE attributions are limited to “Related” or “Not Related”, in this protocol, the “Definitely, Probably and Possibly” attributions will be mapped to the “Related” category.

AEs will be coded into MedDRA preferred terms.

When calculating the incidence of AEs (i.e., on a per subject basis), each subject will only be counted once and any repetitions of AEs within a subject will be ignored; the denominator will be the total population size. All AEs reported will be included in the summaries and analyses.

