[Implementation Note: Day x-y interval should correspond to period of collection for solicited symptoms, in this case Day 1-7. Day y-z interval should be up until subsequent dose, in this case Days > 7.]

MedDRA® System Organ Class	MedDRA® Preferred Term	[Day 1-7] Post Dose 1		[Day 8-28] Post Dose 1		[Day 1-7] Post Dose 2		[Day 8-28] Post Dose 2		Anytime Post Either Dose	
		n	%	n	%	n	%	n	%	n	%
Overall											
Any SOC	Any PT	x	x.x	x	x.x	x	x.x	x	x.x	x	x.x
[SOC 1]	Any PT										
	[PT 1]										
	[PT 2]										
[SOC 2]	Any PT										
	[PT 1]										
[continue for all SOC/PT]	[PT 2]										
Site 1 [repeat for all sites]											
Any SOC	Any PT										

Note: This table presents number and percentage of subjects. A subject is only counted once per PT/Time point.

TABLE 14.3.1.8.2:
Number and Percentage of Subjects Experiencing Related Unsolicited Adverse Events Within 7 Days Post Dosing by MedDRA® System Organ Class and Preferred Term, Dose, Treatment Group, and Site <<Age Stratum>>

CHIKV [Repeat for Placebo] (N=X)

[Implementation Note: Day x-y interval should correspond to period of collection for solicited symptoms, if applicable. In this case, that is Days 1-7.]

MedDRA® System Organ Class	MedDRA® Preferred Term	[Day 1-7] Post Dose 1		[Day 1-7] Post Dose 2		Within y Days Post Either Dose	
		n	%	n	%	n	%
Overall							
Any SOC	Any PT	x	x.x	x	x.x	x	x.x
[SOC 1]	Any PT						
	[PT 1]						
	[PT 2]						
[SOC 2]	Any PT						
	[PT 1]						
[continue for all SOC/PT]	[PT 2]						
Site 1 [repeat for all sites]							
Any SOC	Any PT						

Note: This table presents number and percentage of subjects. A subject is only counted once per PT/Time point.

TABLE 14.3.1.9:
Number of Unsolicited Adverse Events by MedDRA® System Organ Class and Preferred Term, Day Post Dosing, Treatment Group, and Site <<Age Stratum, Overall/Site>>
CHIKV [Repeat for Placebo] (N=X)

[Implementation Note: Day x-y interval should correspond to period of collection for solicited symptoms, if applicable. Day y-z interval should be up until subsequent dose.]

		[Day 1-7] Post Dose 1	[Day 8-28] Post Dose 1	[Day 1-7] Post Dose 2	[Day 8-28] Post Dose 2	Anytime Post Either Dose
MedDRA® System Organ Class	MedDRA® Preferred Term	# of Events	# of Events	# of Events	# of Events	# of Events
Overall						
Any SOC	Any PT	x	x	x	x	x
[SOC 1]	Any PT					
	[PT 1]					
	[PT 2]					
[SOC 2]	Any PT					
	[PT 1]					
[continue for all SOC/PT]	[PT 2]					
Site 1 [repeat for all sites]						

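### SAEs and new chronic conditions to Week 72 are a primary safety endpoint but are only listed, and several unsolicited-AE tables state no onset cut-off that would keep late events out of the four-week endpoint

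*Combined protocol and SAP*

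**What the plan says.** SAP 3.2.1 lists two separate primary safety parameters: "Adverse events through 4 weeks after last injection" and "Serious adverse events and new chronic medical conditions throughout the study". The primary objective in SAP 3.1 is safety and tolerability compared with placebo.

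For the second parameter, SAP 8.4 states: "For reported deaths, SAEs, and new onset chronic medical conditions, the following listings will be presented". It then names Tables 14.3.2.1 (deaths and SAEs) and 14.3.2.3 (new chronic conditions). Both shells in Appendix I have one row per event.

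For unsolicited AEs, SAP 8.3.2 says that everything is recorded until four weeks after the last injection, and then: "At subsequent follow-up visits, only SAEs and new chronic medical conditions will be recorded through the last study visit". SAP 8.3 adds: "All AEs reported will be included in the summaries and analyses". Table 14.3.1.6, the only unsolicited-AE table with confidence intervals and a Fisher test, is headed "Post Dose 1 [Repeat for Dose 2 and Either Dose" and shows no time window. The time-split tables are described in the text as "Subject incidence of AEs over time (Days 1-7, Days > 7". In Appendix I, the shells for Tables 14.3.1.8.1 and 14.3.1.9 use Day 8-28 columns after each dose, plus a column headed "Anytime Post Either Dose".

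Protocol 6.4 says that, in general, variables of interest will be tabulated by vaccine group with point estimates and 95% confidence intervals or percentile spread.

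**The concern.** Two things looked wrong. First, a primary endpoint meant to be compared with placebo has no planned estimate by arm. A reader of the study report would have to count rows in a listing, find the denominators elsewhere and work out the intervals. Yet long-term serious safety is the main return on 72 weeks of follow-up.

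Second, the period of full AE capture and the later period of serious-or-chronic-only capture may be added together in one percentage. If so, the rate printed for the four-week endpoint does not have the time frame that SAP 3.2.1 gives it, and an imbalance in late events could look like an imbalance in early ones.

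**Working it through.** **Inputs.** 200 subjects per arm and 72 weeks of follow-up (SAP 4.1); 180 per arm after the assumed 10% loss (SAP 5); second injection at Day 28 with up to 14 days' allowance (SAP Table 1). The documents give no expected rate of SAEs or chronic conditions, so the event counts and rates in steps 3 and 5 are assumptions.

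**1. The plan's own figure.** SAP Table 2 uses 1 − (1 − p)^180. At p = 1%, 1 − 0.99^180 = 83.62%; at p = 2%, 1 − 0.98^180 = 97.37%. Both match, and this point disputes no printed number. The table is relevant because SAP 5.1 justifies the study size by what can be seen about event rates within an arm and between arms.

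**2. Endpoint against output.**

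| Item | Planned output by arm |
|---|---|
| Unsolicited AEs | Table 14.3.1.6: n, %, 95% CI, Fisher p |
| SAEs, deaths, new chronic conditions to Week 72 | Listings 14.3.2.1 and 14.3.2.3 only |
| Pregnancies | Table 14.3.7: counts by outcome |
| CHIKV cases (exploratory in SAP 10) | Tables 15.1.1-15.1.4: n, %, Clopper-Pearson CI |

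**3. What a by-arm table would report.** Clopper-Pearson 95% limits at n = 200:
- 0 events: 0 to 1.83% (upper limit 1 − 0.025^(1/200))
- 2 events (1%): 0.12 to 3.57%
- 4 events (2%): 0.55 to 5.04%
- 10 events (5%): 2.42 to 9.00%

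At n = 180, 0 events gives an upper limit of 2.03%. For an assumed 3/200 against 0/200, the difference is 1.5 points, Miettinen-Nurminen 95% CI −0.40 to 4.32, Fisher p = 0.25. Exact Fisher power at 200 per arm is 56% for 1% against 5% and 90% for 1% against 7.5%. The table would therefore serve mainly for estimation.

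**4. Which tables are bounded.**
- No onset window and no exclusion of serious events: 14.3.1.6, 14.3.1.7.1, 14.3.1.7.2, and the any-time columns of 14.3.1.8.1 and 14.3.1.9.
- Bounded: the Day 1-7 and Day 8-28 columns of 14.3.1.8.1 and 14.3.1.9, and all of 14.3.1.8.2 (seven days).
- Restricted to non-serious events by their titles: Table 14.3.2.2 and Figures 14.3.1.2 to 14.3.1.5. The SAP restricts by seriousness where it wants to.

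Late events appear to sit in the same data. Listing 16.2.7.2 of unsolicited AEs has a column that flags SAEs, and the note on Table 14.3.2.3 derives chronic conditions from seriousness and outcome codes. Nominally the four-week window closes at Week 8, so 72 − 8 = 64 weeks, or 64/72 = 89% of follow-up, lies beyond it.

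**5. Effect of mixing.** With four-week rate e and late rate l, taken as independent, the printed rate is 1 − (1 − e)(1 − l).

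| e, vaccine / placebo | l, vaccine / placebo | Printed | True difference | Printed difference |
|---|---|---|---|---|
| 30% / 30% | 5% / 1% | 33.5% / 30.7% | 0 | 2.8 points |
| 10% / 10% | 5% / 1% | 14.5% / 10.9% | 0 | 3.6 points |
| 30% / 30% | 2% / 2% | 31.4% / 31.4% | 0 | 0 |
| 10% / 10% | 2% / 2% | 11.8% / 11.8% | 0 | 0 |
| 30% / 20% | 5% / 5% | 33.5% / 24.0% | 10 points | 9.5 points |

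**6. The two late windows.** The text of SAP 8.3.2 and the implementation note on Table 14.3.1.8.1 leave the late window open after Day 7; the column heads close it at Day 28. If dose 2 is given on Day 42, the bounded version leaves up to 42 − 28 = 14 days (Days 29-42 after dose 1) in neither dose's columns. The open version covers those days, but after dose 2 it has no end.

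**The case against.** The strongest reply concerns the mixing. SAP 8.3.2 opens with the four-week recording period for unsolicited AEs, and late SAEs and chronic conditions have their own section, 8.4. The SAP 8.3 sentence on including all AEs closes a paragraph about counting each subject once and about denominators; it does not address time windows. A programmer could reasonably build Table 14.3.1.6 on four-week events only. This stands: mixing is an inference from missing cut-offs, not something that the SAP states.

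A reader might also infer that none of the unsolicited-AE tables has an end date. The documents do not support that, given the Day 8-28 columns and the seven-day table. Those columns do not settle the matter, however, because they contradict the text and give no combined four-week rate, interval or comparison.

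The two halves also pull against each other. If late SAEs do enter Table 14.3.1.6, they are tabulated there by preferred term and arm and are not merely listed. If they do not, that table is clean. Either way, no shell counts subjects with any SAE or any new chronic condition by arm.

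Finally, the trial tests no formal hypothesis, the listings show treatment group and onset date so crude counts can be recovered, and protocol 6.4.2 promises no separate SAE rate table. These points limit the harm. They do not explain why a primary endpoint has no estimate when pregnancies and exploratory CHIKV cases are tabulated by arm.

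**Conclusion.** The missing by-arm summary is explicit in SAP 8.4 and the shells, and should be corrected. It leaves one primary safety parameter without a percentage, interval or difference. The missing onset cut-off is a well-supported ambiguity: the affected tables can absorb events from after the four-week window, but the documents do not show that they will. The conflict between the late windows is plain on the page.

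The size of any distortion is unknown. The 2.8 and 3.6 points in the working rest on assumed late rates of 5% against 1% and on independence of early and late events. Equal late rates raise both arms, create no false difference, and slightly shrink a true one. A reader might go further and conclude that the four-week AE rate could not be interpreted at all, or that neither endpoint would have a usable rate. The documents do not support either conclusion: both require the unfavourable reading of every table, and the bounded columns and listings would still carry usable information.

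**What to change.** 1. Add one safety-population table by arm, Day 0 through Week 72, for any SAE, related SAE, death and new chronic condition. Give n/N, %, Clopper-Pearson 95% CI, and the risk difference with its 95% CI by a named method.
2. Limit Tables 14.3.1.6, 14.3.1.7.1 and 14.3.1.7.2, and the any-time columns of 14.3.1.8.1 and 14.3.1.9, to events with onset from the first injection through 28 days after the last injection. Qualify the SAP 8.3 sentence on including all AEs to match.
3. Reconcile the open-ended window with the Day 8-28 heads, so that the late post-dose-1 column runs to the day of dose 2.

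Items 1 and 2 belong together: the filter alone would remove the only tables in which late SAEs might be counted by arm. The cost is one extra table and a date filter, with no new data.
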